## 6. CONDOR STUDY FLOW DIAGRAM

## 6.0. BACKGROUND AND RATIONALE

### 6.1. THE BURDEN OF END-STAGE RENAL DISEASE (ESRD) AND INADEQUACY OF TRANSPLANTABLE GRAFTS

End-stage renal disease (ESRD) is fatal and in the absence of a kidney transplant, around 50% of the ESRD patients perish within five years due to associated complications . The UK Renal Registry's (UKRR) latest published report revealed that the prevalence of ESRD patients on renal replacement therapy (RRT) in the UK has increased from 700 per million population in 2007 to 1000 per million population in 2017. The one-year survival rate of these patients on RRT aged 60-65 is 85% however; it further declines steeply in the older age groups . Haemodialysis (HD) can provide at best 10% solute clearance of normal kidneys yet it is the commonest form of RRT in the NHS . The ESRD patients on HD have a 17-fold increase in mortality compared to age-matched controls from the general population which is mainly due to premature cardiovascular death .

Keeping in line with the Kidney Disease Outcomes Quality Initiative (KDOQI) clinical guidelines published by the National Kidney Foundation UK recommend that kidney transplantation is the safest and most dependable form of long-term treatment for ESRD patients . The five-year patient survival amongst the transplant recipients is 87% as compared to 30% for the ESRD on HD.

The NHS Blood and Transplant (NHSBT) annual report (2018-2019) revealed that despite a 2% increase in the number of kidney transplants performed that year, there are still 3952 patients on the National waiting list. This is the second highest in the last decade . The unprecedented cessation of transplant activity in the UK due to COVID-19 Pandemic has further increased the shortage of transplant organs .

### 6.2. PROBLEM OF EARLY GRAFT LOSS (EGL)

About 7-10% of the transplanted kidneys are lost to complications in the first three months after transplantation and is termed as early graft loss (EGL). Vascular complications are one of the contributing factors accounting for 30-35% of EGL . Other studies have reported that vascular complications result in 20% of the total kidney grafts lost during the first 30 days after implantation .

[figure not shown]
EGL is a medical catastrophe in kidney transplant recipients with 30-day and 90-day mortality rates of 5.2% and 11.1% respectively . Other studies have reported an increase of 12.28% in the first-year mortality of kidney transplant recipients that suffer EGL. This is due to the physiological stress of returning to dialysis, cardiovascular complications, infections, and morbidity encountered for the removal of the failed graft . Also, EGL is an emotionally devastating outcome for both the patients and the transplant team . About 20% of the National kidney transplant waiting list compromise of the patients that have fallen back after graft loss and activated for re-transplantation that leads to a burden on the limited pool of suitable donor organs . This cascade of complex repercussions also decreases the survival of the patients already present on the transplant waiting list (TWL) who are running out of their dialysis options by increasing the waiting time .

### 6.3. THE PROPOSED TECHNIQUE TO PREVENT THE PROBLEM

Early identification of vascular complications in a kidney transplant is crucial to reduce EGL, as a prompt surgical correction is vital to salvage a compromised graft . However, this can be challenging as in the early stage, the kidney transplant recipients with the vascular complications are clinically asymptomatic and other indicators of graft function like the drop

[figure not shown]
in serum creatinine level and production of urine are unreliable in most cases . The role of the continuous monitoring of graft perfusion can be paramount in the diagnosis of this complication but as yet, no such surveillance device is formally tested in kidney transplant practice .

The implantable Doppler probe is a vascular monitoring device (Figure 1). It produces audible Doppler signals that can be used to monitor blood flow to the attached grafted tissues . Due to the simplicity of its function, it has been used successfully in plastic and breast reconstructive surgery. Following the same principle of vascular monitoring, this device may also be used in kidney transplantation .

**Figure 1:** (a) Cook-Swartz® Implantable Doppler flow probe showing silicon cuff and flexible wire in the background (b) Cook-Swartz® Implantable Doppler flow probe, connecting wire and external monitoring device.

During surgery, it can be attached to the blood vessels supplying the graft (renal artery). The kinetic energy of the blood flowing towards the graft is converted into electric energy and translated into audible Doppler signals (Figure 2). The audible signals are produced continuously till the blood flows in the vessels. The audible signals stop as soon as the blood flow is hampered. This **change in the audible signals is the key** that may suggest vascular complications as they hamper blood supply to the graft. Unless corrected immediately the graft hypoperfusion results in loss of the graft due to irreversible ischemic injury. A compromised graft would require immediate re-exploration if the patient is still in the theatre or further confirmatory radiological investigations (Ultrasound, CT Angiogram) in case the patient has returned to the ward.

**Figure 2:** Cook-Swartz® Implantable Doppler flow probe *in situ* around the renal artery

The application of an implantable continuous vascular monitoring device is quite recent in kidney transplantation. There are only two studies in the medical literature on this topic. The first study was an observational study conducted in 2011 while the other was a follow-up case report published in 2016.

Although conducted in London, these uncontrolled studies have limitations in terms of methodological quality, selection bias, sustained follow-up sample size, level on the hierarchy of evidence in research, descriptive clarity of the study protocol, and measures taken to reduce confounding factors.

Despite the weaknesses, the studies consistently suggest that the monitoring vascular device may have a potential role in kidney transplantation. However, it needs further elaboration and clarity.

#### **6.4. KNOWLEDGE GAP IN EGL:**

Presently the clinicians caring for the transplant recipients postoperatively manage them by the standard care clinical observation. They keep a low threshold for requesting departmental ultrasound scans even for a minimal clinical suspicion of graft hypoperfusion however, there is a tendency to miss cases. A departmental ultrasound scan is a non-invasive radiological investigation that detects vascular complications with a sensitivity of 97%. Nevertheless, this investigation has limitations. It is operator-dependent, has patient limitations if the patient has a high BMI or is uncomfortable due to postoperative pain, takes time to be organised and multiple serial scans are required for continuous monitoring which can be administratively difficult.

Although not widely used in transplant units across the UK, the implantable continuous vascular monitoring device has been used intermittently in our kidney transplant centre for the last nine years. We availed of this opportunity and conducted a service evaluation by undertaking a retrospective evaluation of the prospectively maintained medical notes to describe and compare clinical outcomes in all patients who underwent kidney transplant surgery at our unit with and without this monitoring device. Despite the methodological limitations, the results of this study were suggestive of the usefulness of the monitoring device.

There is a clinical requirement for a reliable continuous vascular monitoring mechanism in kidney transplant surgery. The literature revealed a lack of information and gaps in the evidence on the possible role of a continuous vascular monitoring device in kidney transplantation. Therefore, we propose feasibility RCT with an embedded qualitative study to inform the local practice and provide preliminary information for the definitive future RCT.

## **7.0. AIM OF THE STUDY**

To evaluate the usefulness of an implantable continuous vascular monitoring device in kidney transplant surgery and to inform the protocol development of a definitive planned RCT.

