#### 4. STUDY SUMMARY

Study Title	The role of an implantable Doppler vascular monitoring device in kidney transplant patients: a feasibility randomised controlled trial with an embedded qualitative study.
Short title/acronym	Continuous Implantable Doppler probe monitoring in renal transplant (CONDOR Study)
Study Settings	Southwest transplant centre at Derriford Hospital, University Hospitals Plymouth NHS Trust
Study Design	Feasibility randomised controlled trial with an embedded qualitative study
Study Aim	To evaluate the feasibility of an implantable continuous vascular monitoring device in kidney transplant patients and to inform the protocol development of a definitive RCT.
Study Objectives	
Objectives “1-3” will be met within the feasibility randomised controlled trial:
 
 
1. To assess the capability of vascular monitoring device in the early postoperative period of kidney transplant patients.
 
2. To assess the research methods used to compare vascular monitoring device with the standard care and to estimate surgical outcome measures essential to inform the sample size calculation for the definitive planned RCT.
 
3. To assess the availability of research resources, management support, potential barriers and challenges for the definitive planned RCT.
 
 
Objectives “4” will be met within the embedded qualitative study:
 
 
4. To assess the acceptability of vascular monitoring device in clinical practice and to acquire suggestions and innovative ideas of the stakeholders on refining the design of definitive RCT, functioning of the implantable vascular monitoring device, and improving postoperative patient care.
 

Trial Participants	50 kidney transplant patients (25 in the intervention and 25 in the control group)
Inclusion criteria	
 
• Patients who will have deceased or living kidney donor transplants at the Southwest Transplant Center.
 
• Patients aged 18 years or above.
 
• Patients able and willing to comply with the trial requirements.
 

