## **15. SAMPLE SIZE**

This is feasibility RCT; it is not compulsory to perform a formal power calculation. The sample size is chosen based on the practicalities of conducting a feasibility study. The sample size is a realistic recruitment figure for 24 months based on a recent retrospective study conducted at the Southwest transplant centre leading to this research project. The data suggested that about 65-70 kidney transplants were performed annually in our unit. After exclusion criteria, we anticipate that about 100 patients will be available for recruitment in two-year study duration. The data also suggests that in the last five years there were minimal number of kidney transplant patients that opted not to receive additional vascular monitoring or refused participation after their procedure. This allows us the reassurance of minimum dropout rates in the study.

The COVID-19 pandemic has resulted in an unprecedented increase in our kidney transplant activity. It is due to the reason that the Southwest region has remained the least affected in the UK and our transplant centre remained open. On the contrary, most transplant units across the UK had to be closed down due to infection and resource constraints. This led to the increased

diversion of organ resources to the Southwest transplant centre. As a result, our End-stage renal disease (ESRD) patients availed themselves of the opportunity of more graft offers than usual. This allowed us to perform more transplant surgeries as compared to previous years.

The randomised controlled feasibility trial aims to recruit 50 kidney transplant patients within a 24-month period; 25 in intervention group and 25 in control group. In our study, we propose to attach an implantable continuous vascular monitoring device to half (i.e. 25) of the kidney transplant patients (intervention Group) during their surgery. Postoperatively, these patients will receive graft surveillance by the monitoring device in addition to the standard care clinical observation. The other half (i.e. 25) of the kidney transplant patients (control Group) will receive the standard care clinical observation.

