## 22. DATA ANALYSIS

It is inappropriate to use inferential statistics in feasibility study data to formally test the effectiveness of an intervention. Data analyses using descriptive statistics will be performed in IBM SPSS version 25.0. The means and standard deviations will be

considered as the representative value of the continuous variables (i.e. participant's demographic characteristics) . The categorical variables (i.e. surgical outcomes) will be expressed by frequency distributions (percentages) and elaborated using tables and graphs .

The outcomes for each objective in both groups (i.e. intervention and control) will be summarised using descriptive statistics. The numerical data from both groups will be compared to describe the feasibility of the intervention and generate realistic estimates of important parameters for the definitive multi-centre RCT.

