#### **Risk difference:**

$$\% \text{ in Intervention Group} - \% \text{ in Control Group}$$

By doing so we will note if any substantial change in the outcome of the Intervention Group is observed as compared to the control group. Inferential statistics would be valuable in this regard however they will not be applied due to the study design .

**22.3. OUTCOME MEASURES FOR OBJECTIVE 2:** To assess the research methods used to compare vascular monitoring device against the standard care and to estimate surgical outcome measures essential to inform the sample size calculation for the definitive planned RCT.

The research process assessment will be measured by the selected outcomes. It will determine the suitability of the study methods and procedures adopted in this feasibility study. The outcomes will generate realistic estimates for the definitive multi-center RCT (i.e. eligibility,

recruitment, consent, follow-up rates, etc.). Any limitations or inadequacies will be highlighted for improvement in the latter.

**22.4. OUTCOME MEASURES FOR OBJECTIVE 3:** To assess the availability of research resources, management support, potential barriers and challenges for the definitive planned RCT.

The availability of the research resources and management support in this feasibility study will be evaluated by the selected outcomes. Any limitations or inadequacies will be highlighted for improvement in the definitive multi-center RCT.

The results of the data analysis will be following the CONSORT updated guidelines for reporting feasibility and pilot trials .

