### **36. DISSEMINATION**

The results of this study will be presented at the relevant scientific conferences (i.e. Southwest Annual Transplant day, European Transplant Conference, and the British Transplant Society (BTS) Conference. The findings will also be sent in the form of original research papers to be published in international peer-reviewed scientific research journals.

An internal report will also be presented the Steering Group Committee of the Southwest transplant center. This information will inform the local clinical practice and provide evidence that will be shared with all the transplant units across the UK. Other units will also

be invited to collaborate in the definitive multi-centre RCT that will be supported by on-going patient and public involvement.

The participant's ideas that may lead to improvement in any aspect of the vascular monitoring device will be shared with the manufacturing company and the suggestions for improvement in the postoperative care will be shared with the Steering care group and the Quality improvement team of the Southwest transplant centre.

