Consent forms (fRCT and embedded qualitative study)	2	April 2022 – April 2024 plus secure storage for 10 years. Electronic file erasure will be under data asset owner and steward supervision	This involves consent forms of patients and participants involved in the research	Scanned documents will be stored in the password protected University Hospitals of Plymouth NHS Trust Secure Drive	As per R & D ethical committee policy UHP. It may be shared by the CI with the Steering group committee of the Renal department University Hospitals of Plymouth NHS Trust and the UoP.
Pseudonymised and Processed data in Microsoft Word and Excel Spread sheet analysed with descriptive and analytical statistics. Thematic analysis of qualitative data will be in NVivo software	3	April 2022 – April 2024 plus secure storage for 10 years. Electronic file erasure will be under data asset owner and steward supervision	This involves data not cleared for publication, like anonymised/ pseudonymised and processed data from research with human participants	Microsoft Word, Excel Spread sheet, and NVivo documents will be stored in the password protected University Hospitals Plymouth NHS Trust Secure Drive	As per R & D ethical committee policy UHP. It may be shared by the CI with the Steering group committee of the Renal department University Hospitals of Plymouth NHS Trust and the UoP
Ethical Committee Approval letter	3	April 2022 – April 2024 plus secure storage for 10 years. Electronic file erasure will be under data asset owner and steward supervision	This involves other associated research data and documentation with no value to external users	Word documents will be stored in the password protected University Hospitals Plymouth NHS Trust Secure Drive	As per R & D ethical committee policy UHP. It may be shared by the CI with the Steering group committee of the Renal department University Hospitals of Plymouth NHS Trust and the UoP.

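### Section 7.0 makes the device's usefulness the aim and Section 22.2 plans conclusions about it from 25 v 25 patients, against the feasibility aim in Section 4 and the caution in Section 22

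*Protocol*

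**What the plan says.** The aim is stated twice. The study summary (protocol Section 4) has "To evaluate the feasibility of an implantable continuous vascular monitoring device in kidney transplant patients". Section 7.0 has "To evaluate the usefulness of an implantable continuous vascular monitoring device in kidney transplant surgery". Both go on to say that the study will inform the protocol of a definitive RCT.

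The trial "aims to recruit 50 kidney transplant patients within a 24-month period", with "25 in intervention group and 25 in control group" (Section 15). Objective 1 (Section 20.2) lists four clinical outcomes: early vascular complications, time from implantation to diagnosis, ultrasound scans requested by 24, 48 and 72 hours, and graft survival at three months, counted as grafts lost to vascular complications. None is ranked, called primary or labelled exploratory.

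On analysis, Section 22 states: "It is inappropriate to use inferential statistics in feasibility study data to formally test the effectiveness of an intervention". It limits the analysis to descriptive statistics. Section 22.2 will nevertheless compare percentages by arm in order to note whether the device safely detects vascular complications and averts graft loss. It then computes a risk ratio and a risk difference and adds: "By doing so we will note if any substantial change in the outcome of the Intervention Group is observed". It does not say which outcome counts or how large a change is substantial. It repeats that inferential statistics will not be applied. Section 18.1 sets out the expectation of earlier detection and less graft loss in the device arm and says that the study will test it.

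The document supplied as the SAP is a data management plan. Its dataset table describes the processed data as "analysed with descriptive and analytical statistics".

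**The concern.** Under the feasibility aim, the process rates of Objective 2 (refusal, retention, follow-up) answer the trial's question, and the clinical comparisons only describe. Under the usefulness aim, the Objective 1 comparisons become the answer. The wording of Section 7.0 would matter little if the analysis section ignored it, but Sections 18.1 and 22.2 carry it through.

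Leaving out p-values does not make this safe. A conclusion that the device does or does not avert graft loss, read from raw percentages, is still a conclusion about effectiveness. It simply comes without a measure of its uncertainty. Because no outcome is ranked and no threshold is set, which difference to stress can be settled after the data are seen. A trial that recruits and retains well could be reported as evidence for or against the device on the strength of one or two patients.

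**Working it through.** **Figure to reproduce.** There is no power-based figure. The sample size rests on practicality, which is acceptable in a feasibility trial. The only arithmetic is 25 + 25 = 50, which agrees.

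**Inputs.** Section 6.2 gives early graft loss of 7-10% in the first three months, with 30-35% of it due to vascular complications. Section 15 gives n = 25 per arm.

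**Rate of the graft outcome in Section 20.2(d).**
- Low: 0.07 x 0.30 = 0.021.
- High: 0.10 x 0.35 = 0.035.
- Expected losses per arm: 25 x 0.021 = 0.53 to 25 x 0.035 = 0.88.

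**Chance differences with no device effect.** Let X and Y be independent binomial(25, p) counts in the two arms.
- P(arms differ) = 1 - sum over x of P(X = x)^2. At p = 0.021 this is 1 - 0.452 = 0.548. At p = 0.035 it is 1 - 0.335 = 0.665 (0.6648 unrounded). So the arms differ in about 55-66% of trials, and by symmetry half of these (27-33%) favour the device.
- Most of these differences are a single patient, or 4 percentage points. The device arm has at least two fewer losses in 6.2% (p = 0.021) to 11.2% (p = 0.035) of trials.

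**The planned risk ratio.**
- P(no losses in the control arm) = (1 - p)^25 = 0.588 at p = 0.021 and 0.410 at p = 0.035. The ratio then has a zero denominator, so it is undefined in about 59-41% of trials.
- P(no losses in the device arm and at least one in the control arm) = (1 - p)^25 x [1 - (1 - p)^25]. This is 0.588 x 0.412 = 0.242 and 0.410 x 0.590 = 0.242. In roughly a quarter of trials of a device that does nothing, the risk ratio is therefore 0, which at face value says that every vascular loss was prevented.

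**Precision of the risk difference.** The approximate 95% half-width is 1.96 x sqrt[2p(1 - p)/25], which is 0.079 at p = 0.021 and 0.102 at p = 0.035. That is 8-10 points around a base rate of 2.1-3.5%. The normal approximation is rough at such counts, but the order of magnitude is clear.

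**Other Objective 1 outcomes.** The documents give no rate for complications or scans, so anything here is illustrative. If the complication rate is assumed to be 5-10%, the same formula has the arms differing by chance in 73-81% of trials. No figure is offered for scans, because the answer depends heavily on the assumed scan rate and on whether counts or any scan is compared.

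**The case against.** The strongest reply is that this is one noun. The title, the design, Objectives 2 and 3, the sample-size rationale and the anticipated findings all describe a feasibility study, and both versions of the aim end with informing a definitive RCT. Sections 22 and 22.2 exclude inferential testing, and the protocol commits to CONSORT reporting for pilot and feasibility trials. Section 7.0 may well be a drafting slip, and it changes nothing that is collected. All of this is fair, and it limits the point to interpretation. It does not remove it, because Sections 18.1 and 22.2 say in terms that the study will test, and will note, whether the device reduces graft loss.

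Three stronger readings are tempting, and the documents do not support them.
- *An inflated type I error.* A reader might take "analysed with descriptive and analytical statistics" to mean several uncorrected tests. The phrase describes a file in a storage table, and two explicit protocol statements exclude testing. No alpha is being spent, so family-wise error rates do not apply.
- *The lack of a named primary outcome as a fault in itself.* In a feasibility trial with several process objectives this is missing detail, and which outcomes should decide is partly preference. It matters here only because device conclusions are planned from unranked contrasts.
- *Objective 1 driving a change of practice.* Section 36 says "This information will inform the local clinical practice", but this refers to an internal report on the whole study, including its process and qualitative findings. It is not a rule tied to the arm comparisons.

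**Conclusion.** The point holds as a conflict over what the trial may conclude. Sections 7.0, 18.1 and 22.2 plan a reading of device effect that Section 4 does not ask for and that is at odds with Section 22.

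The size rests on the protocol's own loss figures: with no device effect, a chance difference in vascular graft losses in about 55-66% of trials, and an undefined risk ratio in about 59-41%. These figures assume that the Section 6.2 rates apply to this centre's eligible patients, that outcomes are independent between patients, and that all 25 per arm are followed to three months.

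The trial can run as designed. The wording should be corrected before the data are analysed, so that the basis of its conclusion is fixed in advance.

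**What to change.** 1. Change Section 7.0 to the feasibility aim in Section 4.
2. In Section 22.2, label every Objective 1 contrast exploratory and descriptive, and commit to reporting all of them. Replace the sentence on averting graft loss and the sentence on substantial change with a statement that no conclusion about usefulness, effectiveness or change of practice will be drawn from these contrasts. Amend the statement in Section 18.1 that the expected benefit will be tested, so that it matches.
3. State that the trial's conclusion rests on the Objective 2 feasibility rates already collected: refusal of participation and randomisation (20.3b), and retention and follow-up (20.3c).
4. In the data management plan's dataset table, describe the analysis as descriptive only, to agree with Sections 22 and 22.2.

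The cost is a wording amendment to a few protocol sections and one table cell. It needs no new data, patients or staff. The one loss is that the report can no longer claim usefulness from Objective 1, a claim that 25 patients per arm could not support.
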